**Self- Monitoring Activity: a Randomized Trial of Game-oriented Applications
(SMARTGOAL)**

**Principal Investigator:
[name], MPH
[name]
[contact], [contact]
Email: [contact]**

RESEARCH PLAN

A. HYPOTHESIS AND SPECIFIC AIMS

Physical activity produces health benefits in breast cancer (BC) survivors, including improved quality of life and decreased risk of recurrence and mortality.¹⁻³ However, many breast cancer survivors do not meet activity recommendations,⁴ and racial/ethnic disparities in activity rates⁵ may exacerbate disparities in health outcomes.⁶ Activity interventions among BC survivors improve activity levels in the short term,⁷ but increases are rarely sustained after 6 months.^{8,9} Since habitual activity produces greater quality of life benefits than do briefer increases,¹⁰ creating sustainable interventions should be a cancer control priority.¹¹

Breast cancer survivors consistently include lack of **motivation** as one of their primary barriers to physical activity. Autonomous (volitional) motivation is associated with long-term increases in physical activity.¹²⁻¹⁴ Active video games are a promising medium for intervention with demonstrated ability to increase autonomous motivation,¹⁵ fitness,^{16,17} and quality of life.¹⁸ These games are also acceptable to older¹⁹ and chronically ill adults and women.²⁰ Because of their easy individualization and user-centeredness, games hold the potential for reaching a broad, diverse audience.

Games that include involved narratives may be particularly effective. **Narrative transportation**, or engagement, is highly effective in persuasion to change health behaviors.²¹ Narrative transportation increases enjoyment directly^{22,23} and also likely impacts autonomous motivation by increasing perceptions of autonomy, competence, and relatedness. We hypothesize that narrative-based active games in which users role-play as fit characters will lead to greater autonomous motivation, in turn leading to greater physical activity.

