The goal of this research is to develop a sustainable intervention that is broadly acceptable and efficacious across a diverse population of breast cancer survivors. This study will test a 6-month game-based physical activity intervention among a sample of sedentary, overweight postmenopausal breast cancer survivors. The enhanced intervention will provide a mobile device (iPod touch) and two narrative-based walking game applications (apps). These apps include audio narratives that can change based upon player input and include rich feedback on physical activities. The standard exercise intervention will provide a mobile device with a simple activity monitor and feedback application. Both interventions will include self-monitoring and feedback through the mobile apps and additional feedback through weekly brief counseling phone calls. Thus, comparing the two interventions will allow the investigators to draw conclusions about the unique motivating aspects of the narrative games. A follow-up assessment at 12 months will further allow investigation of intervention effects on activity maintenance over time. The study will address the following specific aims:

Aim 1. Compare a motivationally enhanced intervention to a standard intervention in a 6-month randomized controlled trial. Sedentary, overweight postmenopausal breast cancer survivors (N = 120) will be randomized to the enhanced intervention or to a standard intervention. We will test objective measures of physical activity, physical function, and fitness at the conclusion of intervention contact (6 months) and after a 6-month maintenance phase (12 months).

Aim 2. Compare quality of life and psychological outcomes across the two interventions at 6 and 12 months. We will investigate quality of life (physical, social, emotional, functional, and breast-related), depression, anxiety, and fatigue at 6 and 12 months.

Aim 3. Compare autonomous motivation across the two interventions at 6 and 12 months. Hypothesized psychosocial predictors (Self-Determination Theory constructs and narrative transportation) will also be investigated.

Aim 4. Investigate the cultural appropriateness of the two interventions. At the 6 month assessment or 12 months assessment (if not collected at 6 months), we will conduct brief interviews with participants (N = 120) and stakeholders (N = 10) to investigate acceptability of intervention components. Qualitative analyses will examine racial and ethnic differences.

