The purpose of this study is to test whether an intervention that uses active video games improves upon a standard physical activity intervention. We will test the intervention in a diverse sample of inactive postmenopausal breast cancer survivors. In the short term, the study will provide valuable information about the potential of mobile technology for improving health behaviors, intermediate health outcomes (cardiovascular fitness, physical function etc.), and mood. In the longer term, the results of the study have the potential to improve cancer control on a large scale, and ultimately decrease the morbidity and mortality of BC. If the intervention is ultimately successful, it could be included in survivorship care plans as a standard tool for improving physical activity, benefiting millions of survivors and lowering overall cancer burden. Because the intervention was designed to be easy to individualize, similar programs could easily be targeted to other cancers or chronic conditions.

D. INNOVATION

This project is an innovative step forward for the discipline in several ways: **1)** The primary focus of the intervention is activity maintenance, with a strong theoretical rationale for each intervention component's effect on long-term change. To our knowledge, this will be the first large-scale investigation of the use of video game mechanics in an intervention among older adult cancer survivors. This strategy holds potential for a large

public health impact but has received little research attention. **2)** The individualized and user-centered nature of the intervention may be able to address barriers that contribute to racial/ethnic disparities in physical activity rates and health outcomes. **3)** The intervention incorporates tailoring and patient-centered outcomes in a way that does not decrease the potential ease of dissemination. The applications will allow for simple customization and autonomous choices.

E. PRELIMINARY STUDIES

[name] has extensive experience in the areas of technology and physical activity. The research mentors have been carefully chosen to complement these strengths and to fill gaps in knowledge and experience. The major areas of preliminary evidence for this research study are outlined below.

E.1. Video games and physical activity

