This study is powered to detect differences between the two groups in minutes of moderate-vigorous physical activity at 6 months. We used G*Power to calculate sample size based on several studies that are similar to this one. Similar trials of telephone counseling and activity monitoring among BC survivors produced effect sizes ranging from 0.53 to 0.82.¹⁵⁸⁻¹⁶⁰ Because our study includes a low-intensity control group that we anticipate will produce a weak effect at 6 months, we have powered for a conservative effect size for physical activity at 6 months of approximately $d = 0.65$, which would require an N of 78 for 80% power at an alpha of 0.05. This effect size translates to a between groups difference of approximately 20 minutes per week ($SD = 30$ minutes). An N of 120 would allow a fully powered test of physical activity even in the case of 20% attrition and higher variability than expected (i.e., lower effect size).

Similar studies that investigated maintenance are so few (three to our knowledge) and show such disparate results that power was difficult to calculate for this effect. For example, Rogers et al. report large differences in change scores between groups from baseline to the end of maintenance (79 vs. -22 minutes per week; 3 month follow-up),¹⁶¹ whereas Vallance et al. report smaller differences (24 vs. -14 minutes per week; 6 month follow-up).¹⁶² Even assuming large standard deviations for these change scores, our sample should be sufficient to detect group differences during the maintenance period as well.

F.8. Statistical analysis

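### Does F.7 promise 12-month power that the sample cannot deliver?

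*Combined protocol and SAP*

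**What the plan says.** F.7 opens by stating that the study is powered for the group difference in moderate-vigorous activity at 6 months. It says "we have powered for a conservative effect size for physical activity at 6 months of approximately" d = 0.65, which needs N = 78 for 80% power at alpha 0.05, and continues: "This effect size translates to a between groups difference of approximately 20 minutes per week", with an SD of 30. Enrolling 120 is meant to cover 20% attrition and more variability than expected.

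A second paragraph turns to maintenance. It says that comparable studies are very few, that their results diverge widely, and that power for this effect was hard to calculate. It cites one study with "large differences in change scores between groups from baseline to the end of maintenance (79 vs. -22 minutes per week; 3 month follow-up") and another said to "report smaller differences (24 vs. -14 minutes per week; 6 month follow-up"). It then concludes: "Even assuming large standard deviations for these change scores, our sample should be sufficient to detect group differences during the maintenance period as well".

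F.8 makes the 6-month ANCOVA, adjusted for baseline, the primary analysis. The linear mixed model over baseline, 6 and 12 months is labelled secondary, and one stated purpose is to inform the powering of a subsequent larger trial.

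**The concern.** The two paragraphs of F.7 seem to rest on assumptions that do not fit together. At the end of intervention contact the plan expects a gap of about 20 min/week. Six months after counselling stops, the assurance relies on gaps about two and five times as large. F.7 does not explain why the gap should be wider then, and section A says of earlier trials that "increases are rarely sustained after 6 months". No 12-month SD, target difference or attrition rate is given, and a large SD is not defined.

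Twelve months also matters to this trial. Section D says "The primary focus of the intervention is activity maintenance", Aim 1 tests outcomes at 6 months "and after a 6-month maintenance phase (12 months"), and Table 6.9 lists a 12-month outcomes paper. If the 12-month comparison were underpowered but described as adequate, a non-significant result could be misread as loss of benefit.

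A smaller point is the word conservative for d = 0.65, which lies close to the middle of the cited range of 0.53 to 0.82.

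**Working it through.** **Inputs.** From F.7: alpha 0.05, 80% power, d = 0.65, 20 min/week with SD 30, N = 120, 20% attrition, and change scores of 79 vs -22 and 24 vs -14 min/week. From F.3: equal allocation, 20 per group per cohort. Assumptions: a two-sided test (not stated, but it reproduces the plan's N; a one-sided test gives 60), 20% attrition also at 12 months, no covariate adjustment, and any SD above 30.

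**Method.** Two-sample t-test with noncentral t, n per arm, df = 2n - 2, noncentrality = (difference/SD) × sqrt(n/2).

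**Step 1: reproduce the plan's figure.** At d = 0.65, 39 per arm gives power 0.809 and 38 per arm gives 0.799. So N = 2 × 39 = 78, as stated. With attrition, 120 × 0.8 = 96 completers, or 48 per arm, and power at d = 0.65 is 88%. The 6-month sample size is sound.

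**Step 2: the cited 12-month differences.** 79 - (-22) = 101 and 24 - (-14) = 38 min/week. Relative to 20 min/week these are 101/20 = 5.05 and 38/20 = 1.9.

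**Step 3: the largest SD that keeps 80% power.** The smallest detectable d is 0.5778 with 48 per arm and 0.5157 with 60 per arm. The largest tolerable SD is the difference divided by that d.

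| 12-month difference (min/week) | SD limit, 48 per arm | SD limit, 60 per arm |
|---|---|---|
| 101 (cited) | 101/0.5778 = 174.8 | 195.8 |
| 38 (cited) | 38/0.5778 = 65.8 | 73.7 |
| 20 (the 6-month figure) | 20/0.5778 = 34.6 | 38.8 |

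For the smaller cited difference the limit is 65.8/30 = 2.2 times the only SD in the documents. For the larger it is 174.8/30 = 5.8 times.

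**Step 4: what it takes to produce a shortfall.** Power with 48 per arm:

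| SD | 20 min/week | 38 min/week |
|---|---|---|
| 30 | 90% | >99% |
| 40 | 68% | >99% |
| 50 | 49% | 96% |
| 60 | 37% | 87% |

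With F.7's own difference and its own SD (20 and 30), power is 90%. Power falls well below 80% only when the 6-month difference is carried to 12 months and the SD is raised to 40 or more. Neither value is in the plan for 12 months.

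**Step 5: the label conservative.** The midpoint of the cited range is (0.53 + 0.82)/2 = 0.675, so 0.65 lies slightly below it. At the low end, d = 0.53, power with 48 per arm is 73%. This bears on an adjective; the N of 78 and the 88% power are unaffected.

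**The case for a change.** The strongest case for a change is that 20 min/week is the only difference the protocol plans for, so it is the natural benchmark at 12 months. Against it, the tolerable SD exceeds 30 by only 15% (34.6/30) with 96 completers, or 29% (38.8/30) with no attrition, and nobody would call that a large SD. A dated note in F.7 and a sentence in F.8 would cost almost nothing.

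Part of this stands. The remark would not hold if the 12-month gap were only 20 min/week and the SD well above 35, and F.7 gives no quantified basis for 12 months. A careful author might have limited the remark to differences of 38 min/week or more.

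The rest does not carry. The sentence is restricted to the change scores just cited, and for those it is correct. It follows an explicit admission that power was hard to calculate, and it is hedged. The cited gaps were observed between groups after maintenance and include decline in the comparison groups (-22 and -14), while the intervention-group gain of 24 in the second study is close to 20. Section A's remark concerns increases over time, not the gap between two active arms. The unadjusted test also leaves out the planned baseline adjustment, which could help by an amount that cannot be computed because no correlation is given.

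On the label conservative, the objection is fair that a weak control effect argues for a larger gap and so does not make 0.65 cautious. Whether the cited range transfers to a comparison of two active arms cannot be judged from the documents.

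**Conclusion.** No change follows. F.7 states no 12-month power that the design then misses. Its qualitative remark is true for the differences it refers to, up to a change-score SD of about 66 at 38 min/week or 175 at 101 min/week. These limits assume 96 completers, a two-sided 5% test and no adjustment. The weaker figures, such as 37% power at 20 min/week and SD 60, depend on a target and an SD that the plan does not set for 12 months.

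The proposed note would also alter nothing in the trial. The COVID-19 section says enrolment is complete, so N cannot respond. The 12-month model is already secondary and already meant to inform a later trial. Reporting its group difference with a 95% confidence interval is what analysts would do anyway, and that interval will show how much a non-significant result leaves open. What remains is an editorial preference for a more guarded sentence and a different adjective in a historical sample-size rationale.

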[name] is an expert in muscle metabolism,^{120,121} sedentary behavior,¹²² aerobic exercise,¹²³ and aging.^{124,125} She has conducted numerous clinical trials involving exercise program implementation among older adults. She will assist with conducting objective outcome measures of physical activity, function, and fitness.

Additionally, consultant [name] is an expert in women's health research with extensive experience in recruiting diverse samples of women in the Galveston area for energy balance research.¹²⁶⁻¹²⁸ Several of her research studies have specifically investigated the use of new media for health information among minority women.¹²⁹⁻¹³¹

F. RESEARCH DESIGN AND METHODS

F.1. Overview and study flow

The primary purpose of the SMART GOAL (Self-Monitoring Activity: a Randomized Trial of Game-Oriented AppLications) study is to investigate the impact of an enhanced motivational physical activity intervention among sedentary postmenopausal breast cancer survivors. We will conduct a randomized controlled trial (RCT; N = 120) comparing the enhanced intervention to a standard self-monitoring intervention. The enhanced intervention will consist of provision of two active video games and a mobile device on which to play them. Participants will also receive weekly brief counseling/check-in calls. The standard intervention will consist of provision of an electronic activity monitor and a mobile device, with the same phone call content and schedule.

The trial will be conducted over the course of three years, in three yearly cohorts. Participants in the trial will each attend four visits: a baseline assessment/orientation one week later, an initial counseling/goal-setting

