For the trial, we will recruit participants in three cohorts of 40 participants each, 20 per group, with oversampling of African American and Hispanic women (at least 30% of the sample). Participants will be randomly assigned to receive an enhanced or a standard intervention. Major eligibility criteria will include female gender, postmenopausal status (cessation of menses for at least 12 months), aged 45-75, current inactivity (< 90 minutes moderate-vigorous activity per week), BMI > 25 and < 40, no psychological issues that would interfere with study completion, ability to walk for physical activity, safety of physical activity, and not currently using the monitor/application to be provided. The PAR-Q+ will be used to screen for potential contraindications to exercise ¹³². Endorsement of any of its items will require physician clearance to participate in the study.

Based on incidence data from the Texas Cancer Registry, we estimate that approximately 1950 female breast cancer survivors aged 55 – 75 and diagnosed in the last 10 years currently live in Galveston county, 500 of whom are African-American or Hispanic. We will also sample from nearby counties (including Harris county, which includes Houston). [name] successfully recruited a sample of 60 breast cancer survivors in two years for a physical activity intervention study¹¹² (37% African American and Hispanic) as well as larger samples for cross-sectional research (36% African American and Hispanic).²⁹ Recently, 6 of 10 older adults recruited for a similar study were African American or Hispanic. Thus, we believe our recruitment targets of 40 per year for three years and 30 - 40% minority recruitment (12 or more per year) to be feasible. We will use a combination of advertisement, community engagement, pre-screen via medical record for eligibility and clinic-based solicitation to recruit potential participants. We will sample from Galveston as well as other nearby counties (including at UTMB and MD Anderson clinics in Harris county, which includes Houston, and up to Victoria County). The clinical research coordinator also coordinates a UTMB program that encourages recruitment of ethnic/racial minorities into clinical trials, and has ample experience in recruiting from local communities.

F.4. Enhanced intervention

The intervention consists of several complementary components:

- 1)** Provision of a mobile device (iPod Touch) with armband and headphones

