At baseline, demographic information will be collected regarding gender, race, and age. Cancer-specific information will also be collected regarding time since diagnosis, type/stage of breast cancer, and type of treatment. Participants will complete the Transportability Scale to investigate their tendency towards narrative transportation.¹⁵⁴ We will include treatment status as a covariate in our outcomes models to take into account any variability associated with treatment status.

Acceptability and process measures

Acceptability and usability items will be adapted from Vandelanotte and colleagues.^{155,156} Process measures for both groups will include logs of completed counseling phone calls, attrition, and adverse events. Objective process measures will also be recorded from the two apps. *Zombies, Run!* and Runkeeper will send exercise session information to the *Runkeeper* service, where an interventionist account will "friend" the participant's account. (Participants will not have access to the Runkeeper account.) Number of walks per week, total minutes per week, and steps during walks per week will be abstracted from the website.

For the self-reported measures, participants will have the option to complete them on paper or on a secure website. The same website that houses PROMIS measures can be adapted to include our other questionnaire items for those who choose the Internet option.

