The primary endpoint of this study will be behavioral change in physical activity at 6 months (Aim 1). Our primary hypothesis is: Participants who receive the enhanced intervention will spend more minutes per week in moderate-vigorous physical activity at 6 months than will those in the standard group. To test this hypothesis, we will use an analysis of covariance to test the difference between groups at 6 months, controlling for baseline. Missing data will be imputed. As a secondary analysis, we will use linear mixed modeling to investigate changes in physical activity over time at baseline, 6, and 12 months. This procedure will provide necessary information for powering a subsequent larger trial that will require complex modeling of multiple time points. We will also use multiple imputation techniques prior to all analyses to ensure that missing data due to attrition do not bias our results. Analyses will be performed using SAS 9.2 (SAS, Inc., Cary, NC). [name] and the research assistants will conduct all analyses in collaboration with biostatisticians from the biostatistics key resource in the Institute for Translational Sciences. Outcomes and effect sizes for other variables will be assessed using the same protocol.

Interviews with participants and stakeholders will be transcribed and coded by two trained coders. Code lists will initially be derived from Self-Determination Theory and theories of narrative transportation. Then, coders will use grounded theory to derive codes based on themes brought up by participants.¹⁶³ We have successfully used this procedure in the past.⁹² NVivo qualitative software will be used to code and compare codes across

multiple coders.

F.10. Potential limitations and alternative approaches

Several limitations might hinder the project's progress.

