Participants will be randomized using sequentially numbered opaque sealed envelopes. Group assignments will be written on pieces of paper, placed under a piece of carbon paper, wrapped in aluminum foil, and then sealed one per opaque envelope. The envelopes will be then thoroughly shuffled and numbered sequentially. Envelopes will be assigned to participants after baseline assessment (which will occur after orientation) in order of presentation by a member of the research team blinded to the original randomization process. The participant's ID number will be written on the envelope to ensure that the carbon paper serves as an audit trail.

Questionnaire content

Tables 6.9 and 6.10 display the content of several of the questionnaires to be used in this intervention, to provide context as to the nature of the theoretical constructs measured. All of the measures shown below use Likert-type response scales

Table 6.9. Questionnaire items related to Self-Determination Theory

Motivation	I exercise because other people say I should I feel guilty when I don't exercise I value the benefits of exercise I exercise because it's fun I don't see why I should have to exercise I take part in exercise because my friends/family/partner say I should I feel ashamed when I miss an exercise session It's important to me to exercise regularly I can't see why I should bother exercising I enjoy my exercise sessions I exercise because others will not be pleased with me if I don't I don't see the point in exercising I feel like a failure when I haven't exercised in a while I think it is important to make the effort to exercise regularly I find exercise a pleasurable activity I feel under pressure from my friends/family to exercise I get restless if I don't exercise regularly I get pleasure and satisfaction from participating in exercise I think exercising is a waste of time

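### The primary ANCOVA has no recruitment-cohort term although three cohorts with 20 per group are planned; adding one is a cheap, conditional gain in precision (minor)

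*Combined protocol and SAP*

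**What the plan says.** F.8 defines the primary test of 6-month MVPA: "we will use an analysis of covariance to test the difference between groups at 6 months, controlling for baseline". The secondary analysis is "linear mixed modeling to investigate changes in physical activity over time at baseline, 6, and 12 months", with no covariates named. F.8 applies the same approach to the other outcomes and calls for multiple imputation before all analyses, without listing the imputation variables.

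F.6 (Other variables) adds a covariate: "We will include treatment status as a covariate in our outcomes models to take into account any variability associated with treatment status".

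On the design, F.1 says "The trial will be conducted over the course of three years, in three yearly cohorts", and F.3 says "we will recruit participants in three cohorts of 40 participants each, 20 per group". Section G (Randomization details) describes sealed envelopes: "The envelopes will be then thoroughly shuffled and numbered sequentially". It does not say whether one set of 120 or a separate set for each cohort was prepared, and it mentions neither blocking nor stratification. No section promises a cohort term.

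**The concern.** If the 20-per-group split within each cohort is an allocation rule, cohort is a design factor. Balance within cohort then removes between-cohort variation from the arm difference, but an analysis without cohort still counts that variation in its standard error. The reported interval is wider than the design warrants, and the nominal 5% test rejects too rarely under the null. Some between-cohort variation is plausible: F.10.a allows recruitment to widen to more counties and clinics, F.4 expects new game content, and the COVID-19 procedures arrived late in the trial.

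At stake are calibration and precision for the primary endpoint, and for the other outcomes analysed the same way. The validity of the comparison is not in question.

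**Working it through.** **Inputs.** F.7 gives d = 0.65, alpha 0.05, 80% power, N = 78; a difference of 20 min/week with SD 30; and planned N = 120 with 20% attrition ("An N of 120 would allow a fully powered test of physical activity even in the case of 20% attrition"). F.3 gives three cohorts of 40, 20 per group. The documents do not give the share of residual variance explained by cohort (R²); it is assumed to lie between 0 and 0.20.

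**1. The plan's own figure.** A two-sided two-sample t-test (noncentral t) at d = 0.65 needs 39 per arm, N = 78, with power 0.809. F.7 reproduces. With 120 × 0.80 = 96 evaluable (48 per arm), power is 0.883 at d = 0.65. The figures below use 20/30 = 0.667, so they run slightly higher.

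**2. Cost in degrees of freedom.** With arm, baseline and a binary treatment status there are 96 − 4 = 92 residual df; three-level cohort leaves 90. Analytic power is 0.8983 before and 0.8981 after if cohort explains nothing and is balanced.

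**3. Type I error when arms are balanced within cohort and cohort is ignored.** The true variance of the arm difference is (1 − R²) times what the model estimates, so the actual level is about 2[1 − Φ(1.960/√(1 − R²))]:
- R² = 0.05: 0.0443
- R² = 0.10: 0.0388
- R² = 0.20: 0.0284

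**4. Simulation.** 96 complete cases in three cohorts of 32, baseline slope 0.5, binary treatment status (prevalence 0.3, no effect), 200,000 trials per setting; imputation is not modelled. Power sits a little below the analytic values because baseline and status vary by chance between arms.

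| Allocation | R² | Type I, no cohort | Type I, cohort | Power, no cohort | Power, cohort |
|---|---|---|---|---|---|
| 16/16 in each cohort | 0 | 0.0502 | 0.0504 | 0.8919 | 0.8915 |
| | 0.05 | 0.0446 | 0.0501 | 0.8984 | 0.9071 |
| | 0.10 | 0.0391 | 0.0500 | 0.9031 | 0.9207 |
| | 0.20 | 0.0291 | 0.0504 | 0.9147 | 0.9464 |
| One shuffle, 48/48 | 0 | 0.0497 | 0.0492 | 0.8923 | 0.8853 |
| | 0.05 | 0.0498 | 0.0499 | 0.8909 | 0.9002 |
| | 0.10 | 0.0495 | 0.0500 | 0.8930 | 0.9156 |
| | 0.20 | 0.0499 | 0.0498 | 0.8918 | 0.9411 |

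The 95% CI half-width without cohort is 12.26 to 12.29 min/week. With cohort, as R² goes from 0 to 0.20, it goes from 12.27 to 10.97 (balanced) or from 12.40 to 11.09 (one shuffle).

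**5. Break-even under one shuffle.** Chance imbalance over 2 df uses on average about 2/95 = 0.021 of the information on arm, so cohort must explain about 2% to pay for itself. The simulation agrees: at R² = 0.02 power is 0.8929 without cohort and 0.8921 with it.

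**6. Which allocation?** One shuffle of 60/60 gives exactly 20/20 in all three cohorts with probability C(40,20)³/C(120,60) = 0.0271. The central 95% range for one arm in a cohort of 40 is 15 to 25.

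**The case against.** The strongest reply is that nothing establishes cohort as a stratification factor. Section G mentions no separate envelope sets, and the 20 per group in F.3 stands in a recruitment sentence that may only state the expected split under 1:1 allocation. On that reading the test without cohort is valid, and a cohort term is an optional precision choice whose benefit rests on an R² that the documents do not supply. This stands, and it is why the point is conditional. The 2.7% figure shows that an exact 20/20 split would need a restriction that section G does not describe; it does not show that such a restriction was used.

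Two stronger readings are tempting, and neither is supported:

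- **F.6 and F.8 contradict each other on treatment status.** They do not. The primary ANCOVA is one of the outcomes models to which F.6 refers, and controlling for baseline in F.8 does not exclude a second covariate. The two combine as arm + baseline + treatment status. Repeating it in F.8 is a clarification.
- **Leaving out cohort biases the result or risks a false positive.** It does neither. Allocation is random under both readings, so the arm difference is not biased; the type I error is at or below its nominal level.

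**Conclusion.** Minor; a cheap improvement and not a flaw that endangers the primary conclusion. If arms were balanced within cohort, the F.8 model is conservative, with type I error of about 4.5%, 3.9% or 2.9% at R² of 0.05, 0.10 or 0.20; adding cohort restores 5% and gains about 0.9, 1.8 or 3.2 points of power. If one set of envelopes was shuffled, both models hold their level, and cohort gains precision only above an R² of about 0.02. The lowest power in any setting is 88.5%.

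This rests on the assumed R² range, on 96 complete cases, on the planned effect of 20 min/week with SD 30, and, in the balanced case, on attrition that leaves the arms equal within each cohort.

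**What to change.** Before unblinded analysis:

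- **Primary model in F.8:** 6-month MVPA on arm + baseline MVPA + treatment status + recruitment cohort (three levels). Define cohort in advance from the randomization date, including where anyone randomized after the third year belongs, since F.10.a lets data collection continue into a fourth year.
- **Mixed model:** add treatment status and cohort. Baseline MVPA is already a response there and should not also enter as a covariate.
- **Imputation model:** include arm, baseline MVPA, treatment status and cohort.
- **Clarifications only:** list the categories of treatment status, since F.6 names the source data ("Cancer-specific information will also be collected regarding time since diagnosis, type/stage of breast cancer, and type of treatment") but no coding; and state in section G whether envelopes were prepared as one set or per cohort.

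No new data are needed: enrollment is closed, and cohort follows from existing dates. Cohort uses 2 df. If it explains nothing, the power loss is about zero when arms are balanced within cohort (0.8983 to 0.8981, analytic) and about 0.7 points under one shuffle (0.8923 to 0.8853, simulated). The sample size does not change.
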